7.6.3 Vital Signs

Actual values and the change from baseline to each scheduled visit for each vital sign parameter will be summarized by dose and scheduled visit.

The frequency of systolic and diastolic blood pressure abnormalities based on the:

- Highest-post treatment value
- Last post-treatment evaluation

will be summarized in shift tables. Blood pressure abnormalities are described in Appendix C.

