3.5 Safety

Phase 2 and 3 studies of fostamatinib have been conducted in several indications including ITP, RA and B- and T-cell lymphomas. Doses of fostamatinib have ranged from 50 to 250 mg PO *bid*, depending on the indication being treated. The majority of patients have been treated at doses ranging from 50-150 mg PO *bid*.

The overall pattern of adverse effects of fostamatinib in these various clinical settings (patients with RA, severely ill patients with lymphoma and advanced solid tumours, chronically ill patients with ITP, and in healthy subjects), has been consistent, and includes dose-dependent effects on BP, neutrophil counts, dizziness, GI complaints and liver function test abnormalities, all of which are reversible and manageable with appropriate safety monitoring. The ITP patients (on no anti-metabolites or chemotherapy) have not manifested neutropenia, despite receiving higher doses of fostamatinib than the RA patients. The lymphoma patients have experienced more cytopenias, and infections, consistent with their extensive pre-treatment and underlying disease. In patients with solid tumours, the overall pattern of reported AEs was consistent with a population of heavily pretreated, relapsed patients with solid tumours of varying histologies.

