7.3 Study Follow-Up (Visit 10)

Subjects will be instructed to return to the clinic 2 weeks following the last dose of study drug for Follow-up Study assessments. Haematology, serum chemistry and/or urinalysis are to be performed only if there are clinically significant abnormalities identified in the corresponding panel at Week 24 (Visit 9). If an SAE is present at the last visit, follow-up should occur as indicated in [Section 9.2.1](#).

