7.5.4 Vital Signs

Vital signs (including blood pressure and heart rate) will be assessed at study visits 1b through 10 and extended treatment period visits (blood pressure only). All blood pressure (BP) determinations should be made using an electronic sphygmomanometer with the subject seated. To minimize the ‘white coat effect’, the subject should rest in a quiet room for at approximately 10 minutes prior to taking the BP. The blood pressure should be taken at least 3 times at approximately 5-10 minutes apart, and the lowest of the 3 measurements will be recorded.

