5.8 Multiplicity Considerations

No adjustments for multiplicity will be applied

6. Analytic Definitions

Age at Baseline is the last non-missing age collected before the first dose of study treatment.

Body Mass Index is calculated as $(\text{Weight in kg}/(\text{Height in meter})^2)$. The last non-missing weight and height collected before the first dose of study treatment will be used to calculate the baseline BMI.

Baseline Measurements will be the last measurement for the corresponding variable prior to the first randomized dose at Visit 2. For analysis of the primary efficacy endpoint, the main analysis will be performed with baseline defined as the average between Visit 2 and the most recent screening value prior to Visit 2 (a secondary analysis, with the Visit 2 value alone as baseline, will be performed).

Study Day will be the number of days from first dose date of study drug for the assessments prior to the first dose date to assessment date. That is:

$$\text{Study Day of post-dose assessment} = \text{Assessment Date} - \text{First Dose Date} + 1.$$

$$\text{Study Day of pre-dose assessment} = \text{Assessment Date} - \text{First Dose Date}$$

Pre-treatment assessments could be up to 180 days prior to baseline. If there are more than two pre-treatment assessments for a subject, the last assessments will be used for the analyses related to 'pre-treatment'. Post-treatment assessments will be the assessments after the first dose of study drug. If there are more than two post-treatment assessments for a subject within an analysis visit, the last assessment that is closest to the scheduled study day will be used for the analyses related to 'post-treatment'.

Study Drug Exposure is calculated as number of days from first dose day to last. That is:

$$\text{Study Drug Exposure} = \text{Last Study Drug Date} - \text{First Study Drug Date} + 1.$$

Study Drug Compliance (%) for a subject is calculated as: $100 * (\text{total number of tablets dispensed during the double-blind treatment period} - \text{total number of tablets returned during the double-blind treatment period}) / \text{total number of tablets the subject was supposed to taken during the double-blind treatment period per protocol}$:

$$\text{Compliance (\%)} = 100 \times (\sum_{i=1}^6 D_i - \sum_{i=1}^6 R_i) / \sum_{i=1}^6 T_i * P_i$$

where:

i = study drug dispensation/return visit interval, $i = 1$ to 6

D_i = total number of tablets dispensed for visit interval i

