 - Tubulointerstitial scarring (interstitial fibrosis/tubular atrophy) score
- Frequency of AEs and SAEs by SOC and PT
- Change from baseline in eGFR (mL/min/1.73 m²) at Weeks 12 and 24
- Summary of ALT, AST and total bilirubin abnormalities based on maximum values
- Summary of ALT, AST, and serum creatinine by visit
- Summary of vital signs by visit

Only descriptive statistics for efficacy (and safety) data will be provided at the interim analysis. No inferential statistical analyses will be performed on the efficacy data. Additionally, no imputation will be done for missing data in the interim analysis; only observed data will be reported. Consequently, no adjustment for alpha spending will be made at the completion of the trial.

Listings of the data identified above will also be provided for the Cohort 1 subjects at the interim analysis.

9. Safety Review Committee

Because fostamatinib has been widely used in other treatment settings and its safety profile is well-known, no new safety issues were expected to be identified by this small study. However, because subjects are being treated in a new indication and at higher doses of fostamatinib than used in the large rheumatoid arthritis program from which the majority of prior safety information was collected, an unblinded Safety Review Committee (SRC) was established to periodically monitoring the emerging safety data from the trial. The composition, roles, and responsibilities of the SRC have been defined in a separate SRC charter document.

10. Visit Windows

Assessments will be reassigned to the scheduled visits according to the following visit windows. If there are multiple assessments assigned to the same visit window after the early termination visit reassignment, the non-missing value closest to the scheduled study day will be used. If there

are multiple assessments with non-missing values with the same number of days from the scheduled study day, the latest one will be used.

Table 5: Analysis Visit Window

Scheduled Visit	Study Day	Visit Window (Study Day)
Week 1	7	2 - 10
Week 2	14	11 - 21
Week 4	28	22 - 42
Week 8	56	43 - 70
Week 12	84	71 - 105
Week 18	126	106 - 147
Week 24	168	148 - 180
Week 26	182	181 or Later Not in Extended Treatment

11. Handling of Missing Data

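### The last-value blood pressure shift table mixes on-drug and off-drug readings, and the SAP's visit windows can report off-drug follow-up values as treatment-week values

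*SAP*

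**What the plan says.** SAP 7.6.3 summarises vital signs by visit and adds two blood pressure shift tables, one on the "Highest-post treatment value" and one on the "Last post-treatment evaluation". The governing definition, in SAP 6, is "Post-treatment assessments will be the assessments after the first dose of study drug". It sets no upper limit tied to the last dose.

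Protocol 7.3 has subjects "return to the clinic 2 weeks following the last dose of study drug" for Visit 10, and Protocol 7.5.4 states: "Vital signs (including blood pressure and heart rate) will be assessed at study visits 1b through 10". SAP 10, Table 5, restricts the Week 26 window to subjects not in extended treatment, and SAP 1 limits the plan to the main study. Entry to extended treatment (Protocol 7.11) requires a proteinuria decrease of at least 40% at Visit 9, or a significant biopsy improvement, and having tolerated study drug.

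Table 5 assigns assessments to visits by study day counted from the first dose. Where several fall in one window, "the non-missing value closest to the scheduled study day will be used"; on a tie the latest is taken. Subjects who discontinue study drug have a Visit 9-equivalent withdrawal visit at discontinuation (Protocol 7.9).

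**The concern.** Increases in blood pressure, liver test abnormalities and neutropenia are among the safety parameters of particular interest (Protocol 4.4). Protocol 3.5 describes the drug's effects on blood pressure, neutrophils, liver tests and the gut as "all of which are reversible and manageable with appropriate safety monitoring". For effects of that kind, a reading during dosing and a reading two weeks after dosing answer different questions.

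The last-value table does not keep them apart. Which kind of reading a subject contributes depends on response and tolerability after randomisation, so the mix may differ between arms.

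The windows raise a related problem for early withdrawals. A follow-up reading taken off drug can be labelled Week 8, 12, 18 or 24. It can either displace the reading taken at discontinuation or appear as a treatment visit the subject never reached on drug. For laboratory tests this is selective: Protocol 7.3 has follow-up laboratory panels drawn only when the corresponding Visit 9 panel had a clinically significant abnormality. If that carries over to the withdrawal visit, only subjects with abnormal panels can have the value displaced.

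**Working it through.** **Off-drug gap.** Table 5 puts Week 24 at Day 168 and Week 26 at Day 182. 182 − 168 = 14 days, which agrees with the two weeks in Protocol 7.3. In hours, 14 × 24 = 336. With the R406 half-lives from the renal impairment study (Protocol 3.3.4), 336 / 23.8 = 14.1 and 336 / 19.6 = 17.1 half-lives. Residual drug at 14.1 half-lives is 2^−14.1, under 0.01%. The Visit 10 reading is off drug.

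**Source of the last reading, by subject type.**
- Completer, no extension, attends Visit 10: Week 26 reading, off drug.
- Early withdrawal who attends follow-up: follow-up reading, off drug.
- Extension entrant: no Week 26 window, so Week 24 reading, on drug.

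**Windows for early withdrawals.** Inputs are the Table 5 targets and ranges: Week 1, Day 7 (2–10); Week 2, Day 14 (11–21); Week 4, Day 28 (22–42); Week 8, Day 56 (43–70); Week 12, Day 84 (71–105); Week 18, Day 126 (106–147); Week 24, Day 168 (148–180); Week 26, Day 182 (181 or later). For each withdrawal day w from 2 to 160 (159 days), place the withdrawal visit and last dose on day w and the follow-up on day w + g. If both days share a window with target t, the follow-up is used when |w + g − t| ≤ |w − t|; otherwise the withdrawal value is kept. If the follow-up falls in a later window, it is reported there.

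| Gap g | Replaces withdrawal value | Fills a later treatment week | Follow-up dropped | Off-drug value in a treatment week |
|---|---|---|---|---|
| 11 days | 45 | 64 | 50 | 109 of 159 (69%) |
| 14 days | 41 | 76 | 42 | 117 of 159 (74%) |
| 17 days | 34 | 88 | 37 | 122 of 159 (77%) |

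At 14 days, replacement occurs for withdrawal on Days 43–49, 71–77, 106–119 and 148–160: 7 + 7 + 14 + 13 = 41, or 26% of days. On none of the 159 days does the follow-up reach the Week 26 window.

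**Example.** Withdrawal on Day 72, follow-up on Day 86; both lie in the Week 12 window, 71–105. |72 − 84| = 12 and |86 − 84| = 2, so the off-drug Day 86 value becomes Week 12 and the Day 72 value leaves the by-visit summary.

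**Completers.** Visit 9 within its window (Days 161–175) is at most 7 days from Day 168. Follow-up at Week 26 ± 3 days (Days 179–185) is at least 179 − 168 = 11 days away. Nothing is replaced at Week 24.

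**The case against.** A reader might infer that the plan understates the drug's reversible effects throughout the safety analysis. The documents do not support that. SAP 7.6.3 has a highest-value table that keeps each subject's peak blood pressure. SAP 7.6.2 counts elevated transaminases and Hy's law cases at any time after the first dose. SAP 7.6.1 tabulates adverse events, including those of special interest and those leading to discontinuation, and SAP 7 lists all data by subject. Safety is descriptive only, so no test is affected.

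Nor do the windows always remove the on-drug values of subjects who stopped because of an effect. With a 14-day gap the withdrawal value keeps its own slot on 76 + 42 = 118 of 159 days (74%). Displacement also requires that early withdrawals attend follow-up. Protocol 7.3 is worded for subjects generally, but 7.9 mentions only the withdrawal visit. SAP 10 refers to a reassignment step for early-termination visits without defining it, and that step might prevent some of this.

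The half-life calculation shows that the drug has gone, not that the effect has. The 5 to 7 day recovery in Protocol 3.5.3 is for neutropenia in rheumatoid arthritis patients; no recovery time is given for blood pressure or ALT. Blood pressure after withdrawal also reflects any antihypertensive treatment added meanwhile.

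Finally, a last-value table beside a highest-value table could be meant to show persistence or resolution, and Protocol 10.4 takes safety analysis through Visit 10. That justifies reporting Week 26. It does not justify pooling it with on-drug readings or labelling a follow-up value as a treatment week.

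**Conclusion.** The point holds with limited reach. Applied literally, SAP 6 and 7.6.3 give a last-value table that combines on-drug and off-drug readings according to a response and tolerability criterion met after randomisation, so it cannot be read as a treatment effect. SAP 10 lets off-drug follow-up values stand as treatment-week values on 117 of 159 possible withdrawal days, 41 by replacement and 76 by filling a later week (109 to 122 in total for gaps of 11 to 17 days).

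The counts are shares of possible days, not of subjects. They assume that the last dose is at the withdrawal visit, that early withdrawals attend follow-up, and that the undefined reassignment step does not intervene.

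The effect is confined to the last-value blood pressure table and the by-visit vital-sign and laboratory safety summaries. Dilution towards placebo is plausible there, but its size cannot be computed: the documents give no blood pressure SD, dropout rate, extension rate, or recovery time for blood pressure or ALT. Completers' Week 24 values are unaffected when visits keep to their windows.

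**What to change.** - In SAP 6 and 10, define an on-treatment period ending at the last dose plus a fixed, prespecified margin. It should be long enough to include the Visit 9 or withdrawal visit and shorter than the follow-up gap.
- In SAP 10, assign follow-up assessments after that period to a follow-up window counted from the last dose, whatever the study day, so that they cannot fill or replace a treatment-week value in the vital-sign and laboratory safety summaries. The 117 of 159 days then becomes 0. State what the early-termination reassignment does.
- In SAP 7.6.3, base the table on the last on-treatment evaluation and tabulate the off-drug follow-up reading separately.

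Leave the ITT eGFR efficacy analysis out of this change. Whether off-drug values belong there is a separate choice of estimand.

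The cost is a few sentences in the SAP, a last-dose-date condition in the programming and one additional table. No new data are needed.

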7.6.4 Physical Examinations

The results of physical examinations will be presented only in a by-subject listing

7.7 Analysis of Pharmacokinetic Endpoints

Plasma concentrations of R406 will be summarized by visit using descriptive statistics including the number of non-missing observations, arithmetic mean, standard deviation, geometric mean, median, minimum, maximum, and coefficient of variation for each treatment group in the PK population.

7.8 Analysis of Immunohistochemistry Endpoints

The observed number of macrophages per glomerulus and the change from baseline will be summarized using descriptive statistics by treatment for both extra capillary CD68 macrophages and endocapillary CD68 macrophages.

Change from pre-treatment to post-treatment Syk, Phospho-Syk, Smad 6, and Smad 7 will be evaluated. Other parameters to be included in the analyses will be determined after database lock.

Additionally, the mean number of macrophages per scorable glomerulus and phospho-Syk staining at Baseline will be correlated with change from baseline in sPCR at Week 24.

8. Interim Analysis

An interim analysis of topline safety and efficacy data will be conducted after all of the patients in Cohort 1 have completed their Week 26 follow-up visit. The interim analysis will be performed on the ITT population, but the primary endpoint will only include subjects that completed dosing through Week 24.

The data from all of the Cohort 1 patients will be cleaned and then all Cohort 1 patient data will be hard-locked prior to the interim analysis. A review of all protocol deviations will be performed prior to the hard-lock for the interim analysis and all Cohort 1 patients will be assigned to the various analysis populations before unblinding occurs for the interim analysis. These procedures are intended to minimize potential bias when the final efficacy and safety analyses are performed at the completion of the trial.

Results from the interim analysis will not be used to decide whether to stop or continue the trial based on the efficacy of the 100 mg bid fostamatinib arm. The study's statistical power is expected to be too low mid-way through the trial to make such decisions. Instead, results from the interim analysis will be used to guide business decisions about the further development of fostamatinib for this particular indication.

The interim analysis will summarize the following efficacy and safety results by treatment group:

- Subject disposition
- Demographic and baseline data
- The change in sPCR from baseline by visit
- Summary of sPCR 30% responders by visit
- Summary of sPCR 50% responders by visit
- Summary of sPCR 50% responders at week 24 by visit
- Histologic changes of pre- vs. post-treatment renal biopsies
 - Mesangial hypercellularity score
 - Endocapillary hypercellularity score
 - Segmental sclerosis/adhesion score
 - Global glomerulosclerosis score
 - Tubulointerstitial scarring (interstitial fibrosis/tubular atrophy) score
- Frequency of AEs and SAEs by SOC and PT
- Change from baseline in eGFR (mL/min/1.73 m²) at Weeks 12 and 24
- Summary of ALT, AST and total bilirubin abnormalities based on maximum values
- Summary of ALT, AST, and serum creatinine by visit
- Summary of vital signs by visit

Only descriptive statistics for efficacy (and safety) data will be provided at the interim analysis. No inferential statistical analyses will be performed on the efficacy data. Additionally, no imputation will be done for missing data in the interim analysis; only observed data will be reported. Consequently, no adjustment for alpha spending will be made at the completion of the trial.

Listings of the data identified above will also be provided for the Cohort 1 subjects at the interim analysis.

9. Safety Review Committee

Because fostamatinib has been widely used in other treatment settings and its safety profile is well-known, no new safety issues were expected to be identified by this small study. However, because subjects are being treated in a new indication and at higher doses of fostamatinib than used in the large rheumatoid arthritis program from which the majority of prior safety information was collected, an unblinded Safety Review Committee (SRC) was established to periodically monitoring the emerging safety data from the trial. The composition, roles, and responsibilities of the SRC have been defined in a separate SRC charter document.

10. Visit Windows

Assessments will be reassigned to the scheduled visits according to the following visit windows. If there are multiple assessments assigned to the same visit window after the early termination visit reassignment, the non-missing value closest to the scheduled study day will be used. If there

are multiple assessments with non-missing values with the same number of days from the scheduled study day, the latest one will be used.

Table 5: Analysis Visit Window

Scheduled Visit	Study Day	Visit Window (Study Day)
Week 1	7	2 - 10
Week 2	14	11 - 21
Week 4	28	22 - 42
Week 8	56	43 - 70
Week 12	84	71 - 105
Week 18	126	106 - 147
Week 24	168	148 - 180
Week 26	182	181 or Later Not in Extended Treatment

11. Handling of Missing Data

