During the 24-week double-blind treatment period, subjects should remain on the same dose of ACEi or ARB during the treatment period (Visits 2-9). Subjects will be monitored by		

routine safety assessments (vital signs, haematology, serum chemistries, urinalyses, and adverse event [AE] assessments) and for renal function (spot urine protein/creatinine ratio [sPCR], urine dipstick test for haematuria and estimated glomerular filtration rate [eGFR] using the MDRD equation). At the end of the treatment period, subjects will be encouraged to have a renal biopsy.

Brief Summary of Visit Schedule

There will be 11 visits over the course of 28 to 43 weeks:

- Visit 1a = Up to 120 days prior to Baseline (Visit 2)
- Visit 1b = Up to 30 days prior to Baseline (Visit 2)
- Visit 2 = Day 1, Baseline
- Visit 3 = Week 1 \pm 1 day, Treatment Week 1
- Visit 4 = Week 2 \pm 3 days, Treatment Week 2
- Visit 5 = Week 4 \pm 3 days, Treatment Week 4
- Visit 6 = Week 8 \pm 4 days, Treatment Week 8
- Visit 7 = Week 12 \pm 4 days, Treatment Week 12
- Visit 8 = Week 18 \pm 7 days, Treatment Week 18
- Visit 9* = Week 24 \pm 7 days, Treatment Week 24
- Visit 10 = Week 26 \pm 3 days, Post-treatment

*Visit 9 procedures will be performed for subjects that withdraw early, with the exception that renal biopsy will not be required.

Prior to the completion of this study (ie, before the clinical database is locked and unblinded, and top line efficacy results are available), subjects who have had at least a 40% decrease from Baseline in proteinuria at Visit 9 (or, in the judgment of the Rigel Medical Monitor, a clinically significant improvement in post-treatment biopsy score) and have tolerated study drug may be permitted to continue to receive extended treatment with study drug (fostamatinib or placebo) on the same double-blind treatment regimen until the results of this study are known.

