7.2.2 Treatment Visits 3-9

All visits subsequent to the baseline visit are determined by the date of the baseline visit and should occur within the visit windows specified in Table 2. Over the course of the 24 week treatment period, subjects will be expected to visit the clinic 8 times (including Baseline [Visit 2]). Safety assessments and renal function tests will be performed at each visit to evaluate the safety and efficacy of fostamatinib/placebo, and to determine if a dose adjustment is required. At Week 24 (Visit 9), a percutaneous renal biopsy will be performed and submitted to the central panel of renal pathologists for assessment. This end of treatment biopsy should be collected within 14 days of Visit 9, but is not required to be collected during the visit in which the rest of the Visit 9 procedures are performed. Subjects who withdraw from the study prior to Week 24 will, at discontinuation, have a withdrawal visit equivalent to the Week 24 (Visit 9) assessments (see [Section 7.9](#)), with the exception that the post-treatment biopsy will not be required.

In Austria only, at home urine pregnancy testing will be performed in Weeks 15 and 21 (see Section 7.5.6).

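### SAP Table 5 ends the Week 24 window at Day 180, inside the protocol's Visit 10 window, so a compliant Week 26 reading can be filed as Week 24 and dropped

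*SAP*

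**What the plan says.** **SAP section 10 (Visit Windows).** The rule is: "Assessments will be reassigned to the scheduled visits according to the following visit windows". Table 5 gives Week 24 a nominal Study Day of 168 and a window of Days 148 to 180. Week 26 has nominal Day 182, and its window entry reads "181 or Later Not in Extended Treatment". That is the only row with a condition beyond study day. When several assessments land in one window, "the non-missing value closest to the scheduled study day will be used", with ties going to the latest. The same sentence refers to a reassignment of early-termination visits, but the SAP does not define it.

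**SAP section 6.** "Study Day of post-dose assessment" is the assessment date minus the first-dose date, plus 1.

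**Protocol, follow-up visit.** The synopsis has "Visit 10 = Week 26 \pm 3 days, Post-treatment", and Table 2 gives the same tolerance. Section 7.3 says "Subjects will be instructed to return to the clinic 2 weeks following the last dose of study drug for Follow-up Study assessments". Section 7.9 gives subjects who stop study drug a withdrawal visit with the Visit 9 assessments and does not mention Visit 10. Section 7.2.2, under a heading limited to Visits 3 to 9, says "All visits subsequent to the baseline visit are determined by the date of the baseline visit and should occur within the visit windows".

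**What is measured at Visit 10.** Vital signs are always taken (Protocol 7.5.4). Haematology, chemistry and urinalysis are repeated only after a clinically significant abnormality at Visit 9 (7.3 and Table 2). sPCR is not scheduled. SAP 7.6.3 tabulates vital signs by dose and scheduled visit.

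**The concern.** The analysis window for Week 24 and the permitted window for the post-treatment visit overlap. A site that follows the protocol exactly can hold Visit 10 on a day that the SAP labels Week 24. The reading is off drug and belongs under Week 26, and the table programs would not put it there.

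The Week 1 to Week 24 rows also have no condition on visit label or time since last dose. Any off-drug visit that falls inside one of them is labelled as an on-treatment week.

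At stake is the accuracy of the by-visit vital-signs tables. Blood pressure is a safety parameter of particular interest (Protocol 4.4, SAP 4.4), and Protocol 3.5.1 describes its elevation as a known effect of the drug.

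**Working it through.** **Inputs.** Table 5 nominal days and windows, closest-value rule and tie rule (SAP 10). Tolerances of ± 7 days for Visit 9 and ± 3 days for Visit 10 (Protocol Table 2). Study-day formula (SAP 6).

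**1. Reproduce the nominal days.** 7 × 24 = 168 and 7 × 26 = 182, as Table 5 states.

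**2. Completers: which Visit 10 days are misfiled?**
- On nominal Day 182: 182 ± 3 = Days 179 to 185. The Week 24 row ends at Day 180, so Days 179 and 180 are misfiled: 2 of 7 permitted days.
- Under the +1 formula, a visit exactly 26 weeks after first dose is on Day 7 × 26 + 1 = 183. Then 183 ± 3 = Days 180 to 186, and only Day 180 is misfiled: 1 of 7.

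**3. Which value is used in the Week 24 row?**
- Visit 10 distance from Day 168: 179 − 168 = 11, or 180 − 168 = 12 days.
- In-window Visit 9: Days 161 to 175, at most 7 days away. On the +1 count it is Days 162 to 176, at most 176 − 168 = 8 days away.
- Visit 9 is therefore always selected. The Visit 10 reading is used in neither row. It would supply the Week 24 value only if the Visit 9 reading is missing or lies at least as far from Day 168.

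**4. Early stoppers, only if they return 14 days after the last dose (the 7.3 reading).** With last dose on Day L, follow-up is on Day L + 14:

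| Last dose (L) | Follow-up day | Table 5 row |
|---|---|---|
| 1–7 | 15–21 | Week 2 |
| 8–28 | 22–42 | Week 4 |
| 29–56 | 43–70 | Week 8 |
| 57–91 | 71–105 | Week 12 |
| 92–133 | 106–147 | Week 18 |
| 134–166 | 148–180 | Week 24 |

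The earliest follow-up is Day 15, or Day 12 with a 3-day tolerance, so the Week 1 row (Days 2 to 10) cannot be reached.

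Two examples, with the withdrawal visit on the last-dose day and filed by study day:
- L = 140. The withdrawal visit falls in Week 18 (Days 106 to 147). Follow-up on Day 154 is the only Week 24 value, 14 days off drug.
- L = 110. Both visits fall in Week 18. The withdrawal visit is 126 − 110 = 16 days from target and follow-up (Day 124) is 2 days away, so the off-drug reading is used.

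**5. Check the revised boundary.** With Week 24 = Days 148 to 178 and Week 26 = Day 179 or later, the latest compliant Visit 9 is Day 175 (176 on the +1 count) and the earliest compliant Visit 10 is Day 179 (180). Neither is misfiled on either count.

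**The case against.** The best defence is that little depends on this. An in-window Visit 9 always wins, so a completer's Week 24 value is safe. Safety is descriptive only (SAP 7.6), and windowing by study day regardless of drug status is a common convention. All of that stands, and it is why the point is minor. It does not restore the reading lost from Week 26, which is a plain mismatch between the two documents.

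A reader might infer something stronger: that off-drug readings from early stoppers regularly enter the Week 1 to Week 24 rows. The documents do not support this, for four reasons.
- Section 7.9 reads naturally as an exit visit. Section 7.3 is worded for subjects in general and only implies a Visit 10 after early stopping. If early stoppers have none, only the completer overlap remains.
- SAP 10 does anticipate some handling of early-termination visits. Because that handling is undefined, it cannot be shown to cover Visit 10. Nor can it be assumed that withdrawal visits are filed simply by study day.
- The Week 1 row is out of reach.
- No rate can be given. Going through last-dose Days 1 to 160 with visits on nominal days selects the 14-day follow-up reading on 7 + 14 + 21 + 21 + 28 + 27 = 118 of them. These are calendar days under assumed timing, not subjects, and the documents do not say how many subjects will stop early.

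**Conclusion.** The Table 5 boundary is wrong as written, and the consequence is minor. A Visit 10 held in compliance with the protocol on Day 179 or 180 (only Day 180 on the +1 count) is classed as Week 24 and lost from the Week 26 vital-signs summary. The 2 of 7 and 1 of 7 figures are shares of permitted days, not expected proportions of subjects.

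The early-stopper effect is conditional on a follow-up visit that the protocol does not clearly schedule. If that visit takes place 2 weeks after the last dose, off-drug vital signs enter a Week 2 to Week 24 row whenever the last dose is on Days 1 to 166.

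Conditional repeat laboratory tests, including the creatinine behind eGFR and dipstick haematuria, could be misfiled the same way, but rarely. It would be wrong to infer an effect on the primary endpoint, since sPCR is not scheduled at Visit 10. The adverse-event tables and the highest and last post-treatment blood-pressure tables do not depend on the visit row. No between-arm bias is shown.

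**What to change.** In SAP Table 5:
- End the Week 24 window at Day 178 and start Week 26 at Day 179, keeping the exclusion of subjects in extended treatment.
- Assign any Visit 10 held after early discontinuation by visit label to a separate post-treatment follow-up row, not to Weeks 2 to 24 and not to Week 26. Table 5 has no such row now, and using the Week 26 row would mislabel a reading taken as early as Day 15.
- In the same place, define the early-termination reassignment and say whether it covers Visit 10.

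One case remains. A completer with Visit 9 and last dose on Days 161 to 164 who returns exactly 14 days later is seen on Days 175 to 178, still inside the Week 24 row. Those days precede the protocol's Visit 10 window. Assigning every Visit 10 by label would cover them.

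The cost is a wording change, with no added visits. Some by-visit rows will have slightly fewer values after early stopping. Cohort 1 by-visit tables, already produced through Week 26 for the interim analysis (Protocol 10.9, SAP 8), may need to be re-derived.
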